Energy Supply System	Three						5	-	-	5	5	-	15
	Systems					√							
	Source		√										
Exercise prescription	Conceptual	√					-	-	5	5	5	-	15
	Elements		√	√	√								

Bloom divided the teaching objectives of cognitive activities into six sides: knowledge, understanding, application, analysis, synthesis, and judgment. The first two parts are the learning and understanding of knowledge; the last four parts are applying knowledge. Use six different levels to exam content knowledge

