### 3. Intervention Plan

Table 6. Intervention Plan Design

Group	Experiment Group -Workshop			Control Group - standard teaching teaching		
Week	1-2	3-4	5-6	1-2	3-4	5-6
Content Knowledge Category 	Sports Training Design And Teaching Design	Muscular Functional System And Exercise Physiological System	Competition Venue Planning And Referee Rules	Sports Training Design And Teaching Design	Muscular Functional System And Exercise Physiological System	Competition Venue Planning And Referee Rules
	i) Basketball Weekly Training Plan ii) Basketball Class Hour Teaching Plan	i) Energy Supply System ii) Exercise Prescription	i) Track And Field Venue Planning ii) Basketball Rules	i) Basketball Weekly Training Plan ii) Basketball Class Hour Teaching Plan	i) Energy Supply System ii) Exercise Prescription	i) Track And Field Venue Planning ii) Basketball Rules
Workshop	Workshop Criterion 1			Workshop Criterion 1		
standard teaching	Consistent Criterion					
Duration Time	3 Hours / Total Hours 18			1.5 Hours / Total Hours 18		
Frequency	1 Time / Week			2 Times / Week		
Number Of Week	6 Weeks			6 Weeks		

 Article 27 of the "Interim Regulations on Public Recruitment of Public Institutions". Written test subject category. Primary and secondary school teachers (Class D).

General intervention plan design is an overall overview of the experiment. The whole experiment is divided into two interventions (workshop group and standard teaching group), mainly analyzed from two aspects (same and different). Detailed analysis, one is that the two groups have the same 6-week intervention, the total time is the same, and the intervention content is the same. The second is that it doesn't work. Workshop once a week, once every 3 hours. standard teaching group twice a week, once for 1.5 hours.

Table 7. Intervention Plan-Same Characteristics

Content	Workshop Group and standard Teaching Group
Teacher qualification	Same qualification and titles
	Both have one teacher
	Same teaching experience and research area
Student qualifications	Same age , PE students No students have received this courses prior to the study

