The analysis of intervention Plan-same characteristics mainly includes two parts: Teacher qualification and student qualifications. In the first part, workshop group and standard teaching group, teacher Qualification, same qualification and titles, both have one same teacher majors: physical education, similar experience: minimum more than ten years.No students have received this courses before the study. The second part is the age, major and educational background of students. Students with similar educational backgrounds, aged between 19 and 25, are all majors in physical education.No students have received these courses before the study.

Table 8. Six-weeks Workshop and standard teaching Intervention Details

Week	Content 		Workshop group		Week	standard teaching group
1	Basic theoretical knowledge	Sports training design	Weekly basketball training plan	3H/1time/week	1	Weekly training plan  1.5H / 1 time / week.
						Weekly training plan 1.5H / 1 time / week
2		Teaching design	Class hour basketball teaching plan	3H/1time/week	2	Class hour teaching plan  1.5H / 1 time / week.
						Class hour teaching plan 1.5H / 1 time / week.
3	Health promotion knowledge	Muscular functional system	Energy supply system	3H/1time/week	3	Energy supply system  1.5H / 1 time / week.
						Muscle exercise 1.5H / 1 time / week.
Week	Content 		Workshop group		Week	standard teaching group

 Xia Jinyang. Thinking about the proposition width of sports theory test questions [J]. Sports Culture Guide, 2010,{4}(08):79-82+90.

 Tian maijiu. 《Sports Training》. Beijing: Higher Education Press, July 2006. Chapter 12. Weekly Training Plan and Organization Plan. p369-397.

 Mao Zhenming. School Physical Education, 3rd Edition. Beijing: Higher Education Press, July, 2017. Chapter 8. Physical Education Teaching Design and Plan. Class Hours Teaching Plan (Teaching Plan) 131-142.

 Deng Shuxun. Exercise Physiology. Beijing: Higher Education Press, July 2005. Chapter 1: Energy supply of muscle activity. Three systems of energy supply of muscle activity. P11-20.

 Article 27 of the "Interim Regulations on Public Recruitment of Public Institutions". Written test subject category. Primary and secondary school teachers (Class D).

4		Exercise physiological system	Exercise prescription	3H/1time/week	4	Exercise prescription  1.5H / 1 time / week.

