						Exercise prescription 1.5H / 1 time / week.
5	Physical exercise knowledge	Competition Venue planning	Track and field venue planning	3H/1time/week	5	Track and field venue planning 1.5H / 1 time / week.
						Track and field venue planning  1.5H/1time/week.
6		Referee rules	Basketball rules	3H/1time/week	6	Basketball rules  1.5H / 1 time / week.
						Basketball rules 1.5H / 1 time / week.

This part discusses the details of the 6-weeks workshop and standard teaching intervention. First and foremost, CK includes three categories. The deeper level is divided into six parts; the specific content has methods and plans, Basketball weekly training plan, Basketball class hour teaching plan, Energy supply system, Exercise prescription, Track and field venue planning, Basketball rules. On the other hand, there are two lessons; each class is 1.5 hours.

7 Deng Shuxun. Exercise Physiology. Beijing: Higher Education Press, July 2005. Chapter 3 Physical Fitness and Exercise Prescription. P229-235.

8 Li Hongjiang. Track and Field, Beijing: Higher Education Press, June 2014. Chapter 6 Basic knowledge of track and field. Design and layout of track and field. P104-111.

9 Wang Jiahong. Basketball, Beijing: Higher Education Press, December, 2015. Chapter 17 Referees in Basketball Match. Main Referees in Basketball Match. P291-299.

This is a one-class training plan, mainly divided into other structures. A training session explicitly includes three parts.

To start with, the intervention content Specifically including step 1-An overview, and introduction, step 2-Students formed groups, step 3-Oral test assessment. The first part includes: The teacher introduced the purpose of the study, expectations, and discussion of the principles of sports training design. They were learning content related to design and muscle function and exercise physiology system—rest time.

The second part includes, The teacher introduced the purpose of the study, expectations, and discussion of the principles of sports training design. They were learning content related to design and muscle function and exercise physiology systems. Rest time Divided into three groups and rotated roles of teacher, students, 8 / group. They were learning by the reciprocal peer learning instructional model.

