The third part includes the teacher introduced the purpose of the study, expectations, and discussion of the principles of sports training design. They were learning content related to design and muscle function and exercise physiology systems. Rest time Divided into three groups and rotated roles of teacher, students, 8 / group. They were learning by the reciprocal peer learning instructional model. Students were prompted to switch teacher roles, student every 10 min—evaluation through check sheets and oral test ( 90% or better correct answers ).

On the other hand, time allocation, including specific time allocation.

Table 9. Workshop Methods-Class Hours Teaching Plan

Content	Workshop -Intervention (I) - 3 Hour/1 times / Week		Time-Minute
One lesson Training plan	Part 1 An overview and introduction	a) The teacher introduced the purpose of the study, expectations. b) Discussion of the principles of sports training methods and plans. c) Show the content knowledge in the situation with charts.	4
		3	
		3	
		a) Learning design. b) Muscle function. c) Knowledge of sports physiological system content .	10
	10		
	10		
	Rest time.	10	
	Part 2 Grouping teaching	a) Have group discussions with students. b) Divided into three groups and rotated roles of teacher, students, eight people in each group. c) They are learning by the reciprocal peer learning instructional model.	10
			20
			10
	Part 3 Oral examination assessment	a) Teachers use questions to guide students to think and discuss. b) Students were prompted to switch roles of teacher, student every 10 min. c) Teaching explanation and demonstration. d) Students discuss and reflect.	10
			10
			10
The oral test requires that the correct rate of answers is greater than 90%. a) Encourage students and give good behavioral performance. b) True and false questions performance. c) Essay questions performance.		20	
		20	
20			

Table 10. Workshop Methods-Class Hours Teaching Plan

Content	Workshop -Intervention (II) - 3 Hour/1 times / Week		Time-Minute
Track Meet Rules	Part 1 An overview and introduction.	a) The teacher introduced the purpose of the study, expectations. b) Discussion of the principles of sports training methods and plans. c) Show the content knowledge in the situation with charts.	4
			3
			3
	Part 2 Watching the workshop video clips.	Students are asked to watch instructional videos.	20
		a) Teachers focus on teaching specific steps. b) Common mistakes. c) Correcting mistakes.	10
			5
			5

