This part discusses the details of the 6-weeks workshop and standard teaching intervention. First and foremost, CK includes three categories. Then, the deeper level is divided into six parts: methods and plans, class hour teaching plan, muscle exercise, energy supply, breathing and exercise circulation and exercise, athletic and basketball venue, basketball, and football rules. On the other hand, there are two lessons; each class is 1.5 hours.

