Moreover, different selection. The other section is the threat factor of internal effects in the research. Therefore, it is necessary to distinguish the invariable and the extra changeable variable and control the non-experimental facets: one is variable, and the other is unchanged. The varying experimental factors may be a favorite or unfavorable to the experiment. People have biased opinions and different points of view about everything.

Finally, some measures can be taken based on the above collection of the risk of failure during data. But, first, do an excellent job of equal grouping, and control that everything must be the same except the intervention methods of the workshop and standard teaching .

i) We must do an excellent equal group experiment, divided into the workshop and standard teaching groups. Random sampling uses selective measurement and selection methods. First, before the intervention, pre-test measures the original students' content knowledge level. Then, after measurement, they are sorted according to the scores, ranked according to the sequence position, and equally assigned to each group.

ii) People with attitude bias cannot participate in the experiment. If the experimenter finds himself biased, he should avoid wrong opinions.

iii) The experiment must be recorded in detail. The person in charge of the experiment has to make a detailed record of the experiment as a reference for data sources.

iv) We must eliminate the potential confusion of irrelevant variables, make our research reliable, and draw a compelling inference that the relationship between workshop and students' written test achievements.

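### Table 8, week 3: the second standard-teaching session is labelled muscle exercise, while Table 6 gives both arms the energy supply system, a possible content gap of 0 to 1.5 h on a scored topic

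*Protocol*

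**What the plan says.** Section 3 (Intervention Plan) describes the teaching content in several places.

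- **Table 6** prints the same weeks 3-4 entry for both arms: "i) Energy Supply System ii) Exercise Prescription".
- **The text below Table 6** states that "the total time is the same, and the intervention content is the same".
- **Table 8**, which sets out the sessions week by week, gives the workshop one 3 h session on the energy supply system in week 3. Standard teaching has two 1.5 h sessions that week: the first is on the energy supply system, and the second is "Muscle exercise 1.5H / 1 time / week".
- **The topic list after Table 8** runs "Energy supply system, Exercise prescription, Track and field venue planning, Basketball rules" after its two planning topics. It has no muscle exercise.
- **A different list after Table 11**, tied to neither arm, contains "muscle exercise, energy supply, breathing and exercise circulation and exercise, athletic and basketball venue".

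Section 13, under Validity and Reliability, sets the rule that "everything must be the same except the intervention methods of the workshop and standard teaching".

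On the assessment side, Table 5 (section 2, Design details) has a row "Energy Supply System" carrying 15 points. Hypothesis 2.1 in Table 12 compares the arms on the muscle function system part of the written test.

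**The concern.** The trial is meant to isolate teaching method, so both arms should be taught the same material for the same time. Table 8 is the only place that tells a teacher what to cover in each session, and in week 3 it conflicts with Table 6 and with the statements of equal content.

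A teacher who follows Table 8 literally gives the control arm one session named energy supply instead of two. The visible rows of Table 5 score energy supply and contain nothing on muscle exercise. A difference on hypothesis 2.1 in favour of the workshop could then partly reflect more hours on the examined topic, which is the kind of confounding that section 13 sets out to exclude. The bias, if present, would favour the workshop.

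**Working it through.** **Total hours (Table 6).** Hours = weeks x sessions per week x hours per session.

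- Workshop: 6 x 1 x 3 = 18 h
- Standard teaching: 6 x 2 x 1.5 = 18 h

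Both agree with the stated 18 h. The issue is the content of one session, not total contact time.

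**Topics in Table 8, side by side.**

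| Week | Workshop (3 h) | Control session 1 (1.5 h) | Control session 2 (1.5 h) |
|---|---|---|---|
| 1 | Weekly basketball training plan | Weekly training plan | Weekly training plan |
| 2 | Class hour basketball teaching plan | Class hour teaching plan | Class hour teaching plan |
| 3 | Energy supply system | Energy supply system | **Muscle exercise** |
| 4 | Exercise prescription | Exercise prescription | Exercise prescription |
| 5 | Track and field venue planning | Same | Same |
| 6 | Basketball rules | Same | Same |

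In five of the six weeks the two control sessions share one name. That name matches the workshop topic, apart from the dropped word basketball in weeks 1 and 2. Only week 3 breaks the pattern.

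**Size of the week 3 gap.** Let *s* be the share of the muscle exercise session that in fact covers the energy supply system. The protocol does not give *s*, so it is an assumption, shown over its full range.

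Gap = 3 - (1.5 + 1.5 x *s*) hours

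| *s* | Workshop | Control | Gap |
|---|---|---|---|
| 0 (separate topic) | 3.0 h | 1.50 h | 1.50 h |
| 0.5 (half overlaps) | 3.0 h | 2.25 h | 0.75 h |
| 1 (same material, loose label) | 3.0 h | 3.00 h | 0 h |

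**Scale.**

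- One of 6 x 2 = 12 control sessions is affected: 1.5 / 18 = 8.3% of control time.
- One of six hypotheses (2.1) is touched.
- The visible rows of Table 5 sum to 15 + 20 + 15 + 15 = 65 points. The energy supply row is 5 + 5 + 5 = 15, or 15 / 65 = 23% of those visible. Only four of the six topics appear in the table as read, so this is not a share of the full test.

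**Limits.** These are timetable hours, not minutes on topic. The workshop template in Table 9 includes a 10-minute rest, and its first part lists "Learning design. b) Muscle function" among its items, at 10 minutes each. The protocol gives nothing that links teaching hours to marks, so the hours cannot be converted into a score difference.

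**The case against.** The strongest reply is that this is a stray label and the content is in fact equal.

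- **Source chapter.** The textbook reference for week 3 control teaching (footnote 5) is a chapter on the energy supply of muscle activity, and a second session on it could loosely be called muscle exercise. Each weekly pair of control sessions carries one footnote, and week 3 fits that pattern.
- **Level of the hypothesis.** Hypothesis 2.1 concerns the muscle function system, and Table 8 puts both control sessions in the muscular functional system row. At that level the arms have 3 h each.
- **Workshop content.** The workshop template has its own muscle function item, so its 3 h are not purely energy supply.
- **Loose wording elsewhere.** The control labels omit basketball in weeks 1 and 2. The list after Table 11 names topics, such as football rules and breathing, that are in neither Table 6 nor Table 8, so it looks like leftover text.
- **Clear intent.** Several statements require equal content.

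Much of this stands. It makes the 0 h end plausible, suggests an editing slip rather than a deliberate choice, and rules out anything above minor. It does not remove the contradiction. Footnote 5 is attached to the energy supply entry only. The list after Table 11 names muscle exercise and energy supply as separate items, and the protocol nowhere defines muscle exercise. Even if the intended gap is zero, a teacher working from Table 8 cannot tell.

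**Conclusion.** The point holds as a minor inconsistency. Table 8, week 3, contradicts Table 6, the topic list that follows Table 8 and the stated rule of equal content. Followed as written, it leaves the control arm between 0 and 1.5 h short on the energy supply system. The upper end, half the workshop's timetabled hours on that topic, assumes that muscle exercise is separate material. The lower end assumes that it is another name for the same material.

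Harm to hypothesis 2.1 needs a further assumption: that the muscle function sub-test examines mainly energy supply, as the visible Table 5 row suggests. The other five hypotheses are not affected by this cell.

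**What to change.** Before teaching starts, change the second week 3 standard-teaching session in Table 8 to energy supply system. If the present label is to stay, a note in the cell that the session covers the energy supply system would serve equally well.

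Either edit makes the nominal hours on the topic 3 h in each arm and brings Table 8 into line with Table 6, the list after Table 8 and section 13. The cost is one table cell. No teaching hours are added, and the totals stay at 18 h per arm.

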#### **4.Intervention Plan Summary**

Workshop group refers to the physical or sports education curriculum teaching model. Theme: Sports education curriculum mode: 6 hours of basketball as an example.

Part 1: Teaching Steps: 1. Use diagrams to show combination exercises in situations; 2—Group discussion with students; 3. Teachers use questions to guide students to think and discuss; 4—teaching explanation and demonstration; 5. Student exercises Discussion and reflection.

Part 2: Main features: 1. Give students behavior scores; 2—actual combat situation teaching mode.

Part 3: The actual combat situation teaching curriculum model: a )Motivation, All of the above characteristics can explain why the existing combat situation teaching curriculum model is stimulating.

First of all, real learning content can help students understand the meaning of learning this teaching content. When students know why they do certain things, students may be more willing to participate in the activity. As students become more involved, their skills and knowledge continue to increase. The constant sense of accomplishment may also make them more willing to continue participating in the activity. Second, students can find themselves more, including the sense of belonging to knowledge, technology, and a specific group and improving self-worth and cognition. Third, as students become more adept at the sport, the positive feedback from teachers and the ever-decreasing corrective comments will also make students aware of their progress. Fourth, teachers serve as role models to provide students with mature exercises related to real life. Finally, each situation combination exercise is presented to students in the form of questions. These questions can motivate students to participate and use critical thinking to solve these problems actively.

b) Features of the actual combat situation teaching curriculum model: Cognition and problem-solving-all practical situation- combination exercises solve a problem for students. Decision-making based on issues allows students to learn how to make decisions in a particular game situation:

1) What to do (tactical awareness); 2) How to do it (technical and tactical implementation); 3) When to do it (time); 4) The question of where to do it (space). Adapt to physical and mental development—refers to the teaching content is adapted to the student's age, technical level, cognitive and physical development. All teaching content is excavated from the actual game situation of the corresponding age group, which is representative and can reflect the technical and tactical learning suitable for that age group.

c) What is situational game teaching through Set plays? The state game scene can be expressed as a pre-defined relationship action plan, including rules, player positions, blank areas, techniques, strategies, and tactics. In this model, technologies and processes are planned in detail according to the level of development. Techniques and procedures are fully integrated with other variables in the game and learned from the state of the game scene. Therefore, skills are not isolated but holistic and related. The situation of every situational game is accurate, and it reflects the status of the game. Students studying physical education can use their skills in extracurricular sports and recreational activities without losing meaning in a precise learning environment.

## **5. Location**

The Ning Xia University of China. In terms of students, the proportion of people who choose to work is high, while the proportion of people who choose to continue their postgraduate entrance tests is negligible. Sports graduates account for 70% of Ning Xia Province, and students have not participated in workshop study. On the school side, the school has perfect teaching equipment to meet the experimental requirements, conducive to better completion.

## **6. Measurement and Instrumentation**

This part discusses the specification allocation, processing, instruments used—highlights on the instruments or their description. The specific analysis is as follows. First, the definition of daily instruments: including learning task list, student attendance sheet, student score sheet, Teaching intervention plan design, workshop method-class teaching plan, standard teaching -class teaching plan, population and sample scale, daily observation file, observation record sheet, notebook, pen, and notebook. Second, description of Written test instrument: it includes achievement test, score test table, two-way decomposition table, diagnostic test table, test reliability analysis table, data analysis table, and written test paper. Third, necessary instrument description, microphone, slide photography, camera, electronic whiteboard, classroom, projector, video camera, tape recorder, mini-classroom, multimedia classroom, and daily appliances.

